number of bacteria in the lungs or that it reduces inflammation in the lungs and the upper airways. Neither of these theories are proven and there has been a different mechanism suggested, although it has been much less studied. Azithromycin is thought to encourage the body to move food and fluid through the gut more quickly, and this may help to prevent small food particles and stomach to reflux into the airways. It has been shown that lung damage can occur when gut contents enter the airways, which may contribute to the symptoms of patients with chronic lung disease.

In this trial we will be testing the effect of azithromycin on the gut in patients with chronic lung diseases. We will measure the strength of a patients swallow by measuring the pressures in their gullet, using high-resolution oesophageal manometry (HROM), before and after treatment with azithromycin. We will also measure the effect that azithromycin has on their symptoms and observe whether there is a relationship between the strength of their swallow and their symptoms.

At the end of this study, we will hope to better understand the way in which azithromycin helps to improve the symptoms of patients with chronic lung diseases. We also hope to open the door to investigate the effect of other drugs that improve gut function in patients with chronic lung diseases.

PROTOCOL SYNOPSIS

Sponsor	Hull University Teaching Hospitals NHS Trust	
Intervention	Pilot study	
intervention		
Trial Number	IRAS ID: 1006318	
Title of Study	Exploring the effect of Azithromycin on oesophageal motility and respiratory symptoms in patients with chronic respiratory disease: a prospective observational study	
Trial Centres	- Castle Hill Hospital, [name]	
Phase of Development	Pilot	
Objectives	Aim : To investigate the feasibility and acceptability of High-resolution oesophageal manometry (HROM) in the diagnosis and treatment strategies of chronic respiratory diseases. Exploratory analysis will be performed on the effect of azithromycin on oesophageal motility and how it relates to symptomatic improvement in patients with chronic respiratory disease who are being commenced on azithromycin as part of routine clinical care.	
	Objectives: Specific trial objectives will address both the feasibility and acceptability outcomes as well as exploratory outcomes	
	Feasibility outcomes	
	Recruitment: eligibility to consent ratio, recruitment rate, and participant retention to follow-up.	
	2. Data quality: Completion of clinical outcomes at follow-up and patterns of	
	missing data for the trial measures. Completion of participant symptom questionnaires throughout the study. Completion of trial processes, principally HROM.	
	3. Acceptability of assessment: Quantify the proportion of participants who judge the trial investigations, principally HROM, to be acceptable.	
	Exploratory clinical outcomes	
	1. Oesophageal functioning: To evaluate the effect of azithromycin on the contraction vigour and swallow coordination. This will be evaluated by investigating patients with HROM before and 1 month after initiation of azithromycin as part of routine clinical care.	
	2. Symptom burden: Symptoms will be assessed before and 1 month after initiation of azithromycin as part of routine clinical care. Symptoms will be measured using validated symptom questionnaires, visual analogue scale for cough, and numeric rating scales for breathlessness	

	 Relationship between oesophageal motility and symptoms: The change in oesophageal functioning and presence of respiratory symptoms will be examined in each participant. The relationship between these two parameters will then be examined using statistical analysis. Effect of azithromycin therapy on continuous objective cough frequency as measured by the Hyfe Cough Tracker©. Relationship between continuous objective cough frequency data and subjective repetitive cough evaluation as measured by cough VAS.
Trial Design	A prospective pilot trial of a single group of patients with chronic respiratory disease being investigated with HROM and treated with azithromycin as part of routine clinical care.
Number/Type of Participants	Thirty individuals with chronic respiratory disease who are being commenced on azithromycin as part of routine clinical care.
Inclusion Criteria	 Males and females aged ≥18 years. Have a diagnosis of chronic respiratory disease (COPD, asthma, interstitial lung disease, chronic cough, cystic fibrosis, and/or bronchiectasis) confirmed by a consultant respiratory physician. Exhibit symptoms consistent with airway reflux, demonstrated by a score ≥14 on the Hull Airways Reflux Questionnaire Are being initiated on azithromycin treatment as part of routine clinical care by their usual clinician. This will include all common treatment regimes, 250mg once daily, 250mg three times per week, and 500mg three time per week. Are willing and able to consent to all trial procedures.
Exclusion Criteria	 Previous treatment with long-term macrolides in the past 3 months. Unable to be investigated with HROM due to contraindications such as anatomical abnormalities or diseases of the oesophagus or unwilling/unable to be investigated with HROM based on the clinical judgement of the investigators due to severity of lung disease. Have another cardiorespiratory cause for their symptoms (such as heart failure or lung cancer). Are unable or unwilling to consent to or complete the trial procedures. Women of child bearing potential not using effective means of contraception. Effective methods of contraception include any oral contraceptive pill, any intrauterine device, any long term contraceptive implant, and any long-acting contraceptive injection Have been involved in another medicinal trial (CTIMP) within past four weeks.

Trial Treatment(s)	Trial Participants will be commenced on azithromycin therapy as part of usual clinical care.
Trial Endpoints and Statistical Methods	For trial endpoints, appropriate statistical analysis will be performed to compare HROM metrics and symptom questionnaire data at baseline and at follow-up.
	A table showing baseline demographic and clinical characteristics for each group will be presented. Participant characteristics will be summarised using appropriate statistics. Medians (interquartile range) will be reported for ordinal data, mean (standard deviation) for continuous data and raw count (number, %) will be reported for nominal data.
	For participant outcome data, descriptive statistics, mean (standard deviation) for continuous outcomes and raw count (%) for categorical outcomes, will be reported for each group at baseline and at 1-month follow-up, and for continuous objective and subjective cough data where applicable.
Safety Analyses	AEs/SAEs will be listed and summarized using descriptive statistics.
Sample Size Rationale	As this is a pilot study, a formal sample size calculation has not been performed. We will recruit 30 participants over 12 months based on National Institute for Health Research recommendations for pilot/feasibility studies.

SCHEDULE OF ASSESSMENTS AND PROCEDURES

Visit	Screening Visit	Baseline visit		Follow up visit
Day	-28 to -7	0		28 to 42
Procedure/Assessment			mi i	
Written Informed Consent	Х			
Inclusion/ Exclusion Criteria	Χ	Х		
Invitation Experience survey	Χ			
Setup of the Hyfe Cough Tracker©	Χ			
Monitoring of cough frequency using the Hyfe Cough Tracker©	X**	Х		Х
Vital signs		Х	apy	Х
Weight and Height		Х	her	Х
Physical Examination		Х	n t	Х
Electrocardiogram		Х	yci	Х
Past Medical History		Х	m	
Review of previous laboratory results		Х	ᆴ	
AE Monitoring		Х	azi	Х
			0	
MRC Dyspnoea grade		X	n t	X
Hull Airway Reflux Questionnaire	Х	Х	om [Х
Breathlessness, Cough, and Sputum Scale		Х	Minimum 1 month on azithromycin therapy	Х
St George's Respiratory Questionnaire		Х	ן שַׁ ן	Х
Leicester Cough Questionnaire		X*	i	X*
King's Brief Interstitial Lung Disease Questionnaire		X*	Σ	Χ*
COPD Assessment Test		X*		X*
Asthma Control Questionnaire		X*		X*
Visual Analogue Scales (Cough)		Х		Х
Numeric Rating Scale (Breathlessness)		Х		Х
Spirometry		Х		Х
High-Resolution Oesophageal Manometry†		Х	 	Х
Health Care Utilisation				Х
Evaluation of usual care received				Х
Trial Experience Survey				Х

^{*}Questionnaires will be administered dependent on patients' main respiratory diagnosis.

^{**}If willing, patients would have the possibility to begin objective unobtrusive continuous cough monitoring after the screening visit.

[†]Patients will be eligible if they have had HROM performed up to 3 months prior to screening, however they must not have been treated with macrolide antibiotics during this time.

TRIAL FLOW CHART

Day -28 to -7

[figure not shown]
Consent
Inclusion/Exclusion Criteria
Invitation Experience Survey
Hull Airway Reflux Questionnaire
Setup of Hyfe Cough Tracker© equipment and
download of Hyfe Research© smartphone app

Day 0

Inclusion/Exclusion Criteria
Hull Airway Reflux Questionnaire
Physical Examination
Vital Signs
Spirometry
ECG
HROM
Past Medical History
Questionnaires as per schedule and based on patients primary diagnosis
Review of Hyfe Research© app data

Day 28-42

Inclusion/Exclusion Criteria
Hull Airway Reflux Questionnaire
Physical Examination
Vital Signs
Spirometry
HROM
ECG
Past Medical History
AE Monitoring
Questionnaires as per schedule and based on patients primary diagnosis
Review of Hyfe Research© app data

LIST OF ABBREVIATIONS

Define all unusual or 'technical' terms related to the trial. Add or delete as appropriate to your trial. Maintain alphabetical order for ease of reference.

AE Adverse Event

AECOPD Acute Exacerbation of COPD

AR Adverse Reaction

CA Competent Authority

CC Chronic Cough

COPD Chronic Obstructive Pulmonary Disease

CRF Case Report Form

CTA Clinical Trial Authorisation

CTIMP Clinical Trial of Investigational Medicinal Product

DSUR Development Safety Update Report

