2. TRIAL AIMS AND OBJECTIVES

Aim: To investigate the feasibility and acceptability of HROM in the diagnosis and treatment strategies of chronic respiratory diseases. Exploratory analysis will be performed on the effect of azithromycin on oesophageal motility and how it relates to symptomatic improvement in patients with chronic respiratory disease who are being commenced on azithromycin as part of routine clinical care.

Objectives: Specific trial objectives will address both the feasibility and acceptability outcomes as well as exploratory outcomes.

Feasibility outcomes

- 1. Recruitment: eligibility to consent ratio, recruitment rate, and participant retention to follow-up.
- 2. Data quality: Completion of clinical outcomes at follow-up and patterns of missing data for the trial measures. Completion of participant symptom questionnaires throughout the study. Completion of trial processes, principally HROM.
- 3. Acceptability of assessment: Quantify the proportion of participants who judge the trial investigations, principally HROM, to be acceptable.

Exploratory clinical outcomes

- Oesophageal function: To evaluate the effect of azithromycin on oesophageal contraction vigour and swallow coordination. This will be evaluated by investigating participants with HROM before and 1 month after initiation of azithromycin as part of routine clinical care.
- Symptom burden: Symptoms will be assessed before and 1 month after initiation of azithromycin as part of routine clinical care. Symptoms will be measured using validated symptom questionnaires, visual analogue scale for cough, and numeric rating scales for breathlessness
- 3. Relationship between oesophageal motility and symptoms: The change in oesophageal functioning and presence of respiratory symptoms will be examined in each participant. The relationship between these two parameters will then be examined using statistical analysis.

4. Effect of azithromycin therapy on continuous objective cough frequency as measured by the Hyfe Cough Tracker©.

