4.2 Exclusion Criteria

- Previous treatment with long-term macrolides in the past 3 months.
- Unable to be investigated with HROM due to contraindications such as anatomical abnormalities or diseases of the oesophagus or unwilling/ unable to be investigated with HROM based on the clinical judgement of the investigators due to severity of lung disease.
- Have another cardiorespiratory cause for their symptoms (such as heart failure or lung cancer).
- Are unable or unwilling to consent to or complete the trial procedures
- Women of child bearing potential not using effective means of contraception. Effective methods
 of contraception include any oral contraceptive pill, any intrauterine device, any long term
 contraceptive implant, and any long-acting contraceptive injection
- Have been involved in another medicinal trial (CTIMP) within past four weeks.

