5.3 High-resolution oesophageal manometry protocol

All participants will be investigated using a standardised HROM technique. Participants will be advised to fast 4 hours prior to investigation and will be investigated with a 36-channel combined

manometric and impedance monitoring catheter. This catheter will be inserted trans-nasally to a length of 60cm from the nostril. Participants will then be asked to lay supine for 5 minutes prior to measurement.

A standardised protocol of oesophageal function tests will be followed, with further tests utilised if felt appropriate by the clinical scientist performing the test. The mandatory tests include:

- 10 separate swallows of 5mls of water with an interval of 15 seconds between each swallow.
- The participant will then be asked to complete 5 rapid swallows, ingesting 2mls of water at each swallow.
- The final test will consist of the participant swallowing 5 small pieces of white bread in 5 separate swallows.

Each trial will be analysed manually by an expert gastrointestinal physiologist and a full analysis report will be produced each individual trial in each participant.

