7.1 Participant Recruitment and Consent

Potential participants will be identified from the Hull University Teaching Hospitals NHS Trust respiratory medicine outpatient department. Participants will be eligible for screening if their usual treating clinician feels it appropriate to initiate long-term azithromycin treatment as part of their usual NHS care. Patients can be included in the trial if they have already undergone HROM investigation in the past 3 months prior to identification and are being initiated on long-term azithromycin treatment, however patients cannot have been taking azithromycin at the time of their previous HROM investigations.

All participants will be given adequate time to consider the trial and formulate questions. Any questions will be addressed and answered fully by the PI or delegated trial doctor. An actual period is not specified. All potential participants will be given a Participant Feedback Questionnaire to complete and return.

The PI retains overall responsibility for obtaining informed consent of participants at site and must ensure that any person delegated responsibility to participate in the informed consent process is duly authorised, trained and competent to participate according to the ethically approved protocol, the UK clinical trial regulations, GCP and the Declaration of Helsinki.

Only delegated trial doctors will be allowed to take consent in this study. All consent forms will be completed and stored in accordance with local ethics and general data protection regulation requirements.

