7.3 Screening Visit (Day -28 to -7)

Suitable participants who have been identified on specialist assessment by the HUTH respiratory medicine department or the trial team will be screened for eligibility and will obtain informed consent if eligible. If the participant agrees to take part in the study, they will undertake screening. The following procedures will be performed during this visit:

Eligibility Assessment:

- Review of inclusion and exclusion criteria
- Consent if eligible
- Participant invitation experience questionnaire*
- Hull Airway Reflux Questionnaire
- Set up of the Hyfe Cough Tracker© device
- Cough VAS

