7.4 Baseline Assessment Visit (Day 0)

Participants will be invited to attend the Respiratory Medicine Clinical Trials Unit at Castle Hill Hospital for baseline assessment visit within 1 month of screening. Participants who have not had an HROM performed within 3 months prior to screening will also undertake their initial HROM investigation during this visit.

Baseline Assessments:

- Medical history
- Review of previous laboratory results (provided they have been performed as part of routine clinical care in the 3 months prior to recruitment):
 - o Blood Haemoglobin level
 - Total blood white cell count
 - Total blood eosinophil count
 - Blood alanine transaminase
 - Blood alkaline phosphatase
 - Blood bilirubin level
 - o Blood albumin level
 - Sputum microscopy, culture, and sensitivity results.
- Physical examination
- Monitoring of vital signs
- Weight and height
- Electrocardiogram
- Spirometry
- BSCC
- HARQ
- MRC Dyspnoea Scale
- St George's Respiratory Questionnaire
- Disease-specific symptom questionnaires
- Disease-specific quality of life questionnaires
- Cough Visual Analogue Scale
- Monitoring of cough frequency using the Hyfe Cough Tracker
- Initial HROM investigation as per the HROM protocol in section 6, performed by a clinical scientist specialising in GI physiology.

*All individuals undergoing screening will be asked to complete an anonymous survey ('Invitation Experience Survey':) whether they consent to take part in the trial or not. If participants agree to complete the questionnaire this will be taken as implied consent for the information they provide in the survey to be used for the purposes of this study. This survey will be completed with the help of a member of the trial team and stored in the site file.

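### A pre-trial HROM may stand in for the Day 0 baseline, with differing time anchors and macrolide conditions, so HROM change and symptom change can cover different periods

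*Protocol*

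**What the plan says.** The footnote to the HROM row of the Schedule of Assessments and Procedures reads "Patients will be eligible if they have had HROM performed up to 3 months prior to screening", and adds that there must have been no macrolide antibiotic treatment in that period. Section 7.4 makes the substitution explicit: "Participants who have not had an HROM performed within 3 months prior to screening will also undertake their initial HROM investigation" at the baseline visit. Anyone with a recent test has none at Day 0.

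Section 7.1 describes the same allowance differently. It admits patients who have "already undergone HROM investigation in the past 3 months prior to identification", and its drug condition is "however patients cannot have been taking azithromycin at the time of their previous HROM investigations". Section 4.2 has a general exclusion for all participants: "Previous treatment with long-term macrolides in the past 3 months".

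Section 2 describes the motility outcome as "HROM before and 1 month after initiation of azithromycin". Section 5.3 states "All participants will be investigated using a standardised HROM technique" and lists mandatory swallow tests. Section 11 compares baseline with follow-up HROM and questionnaire data by paired tests and does not mention the age of the baseline HROM. Section 6.1 makes completion of trial processes, chiefly HROM, and the acceptability of HROM part of the primary feasibility outcomes.

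**The concern.** Questionnaires are always taken at Day 0, but the baseline HROM may come from months earlier. For participants who enter this way, the HROM change and the symptom change describe different periods, and only the last part of the HROM interval is on azithromycin. Sections 6.3.1 and 6.3.2 and exploratory objective 3 relate these two changes to each other. In a single-arm study of 30, drift in motility before treatment cannot be separated from a treatment effect, and it cannot even be examined unless the date of the baseline HROM is recorded.

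Macrolide exposure matters for the same reason. Section 1 attributes motility effects to macrolides as a class and names erythromycin as a motilin receptor agonist. If the passages disagree on which exposure is allowed, some baselines may not be untreated ones.

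There is also a feasibility question. People who arrive with a completed HROM have already tolerated the test, and the protocol does not say whether that test counts as a completed trial process.

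**Working it through.** **Inputs.** Look-back of 3 months before screening, taken as 90-92 days (schedule footnote). Screening from Day -28 to Day -7 (Section 7.3). Follow-up 28-42 days after azithromycin is started (Section 7.5); I assume the start is Day 0.

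**The plan's own interval.** For an HROM done on Day 0, the HROM-to-HROM interval is 28-42 days, the same as for symptoms. This reproduces.

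**The longest permitted interval with an earlier HROM.**
- Age at Day 0: 90 + 28 = 118 to 92 + 28 = 120 days, about 3.9 months.
- Age at a Day 28 follow-up: 118 + 28 = 146 to 120 + 28 = 148 days.
- Age at a Day 42 follow-up: 118 + 42 = 160 to 120 + 42 = 162 days, about 5.3 months.
- Ratio to the symptom interval at the same visit, with the 92-day look-back: 162/42 = 3.9 and 148/28 = 5.3.
- Share of the HROM interval on azithromycin at that extreme: 42/162 = 26% and 28/148 = 19%.

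These are upper limits. An HROM done on the day of a Day -7 screening visit gives 7 + 28 = 35 to 7 + 42 = 49 days, close to the symptom interval. On Section 7.1's anchor no upper limit can be computed, because the gap from identification to screening is not fixed.

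**The macrolide conditions side by side** (exposure within the 3-month look-back):

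| Patient | Schedule footnote | Section 7.1 | Section 4.2 |
|---|---|---|---|
| No macrolide | passes | passes | passes |
| Short macrolide course after the earlier HROM | fails | passes | passes |
| Short course of a macrolide other than azithromycin during the earlier HROM | fails | passes | passes |
| Short azithromycin course during the earlier HROM | fails | fails | passes |

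A patient can satisfy all three, but the middle two rows get different answers from the footnote and from Section 7.1.

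**HROM completion, on assumed values.** Let k of 30 enter with a prior HROM that is counted as complete, and let p be true completion of the first HROM among the rest. Reported completion is (k + (30 - k)p)/30, and the excess over p is k(1 - p)/30. Neither k nor p is in the protocol.
- p = 0.80: k = 5, 10, 15 gives 83.3%, 86.7%, 90.0%, an excess of 3.3, 6.7, 10.0 points.
- Over p = 0.70 to 0.90 and k = 5 to 15, the excess runs from 5 × 0.10/30 = 1.7 points to 15 × 0.30/30 = 15.0 points.
- With k = 0, or with prior tests left out of numerator and denominator, it is zero.

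**The case against.** Several stronger readings are tempting, and the protocol does not support them.

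- A reader might infer that the objective is contradicted. It is not: an older HROM is still before initiation, and follow-up is still 28-42 days after it. Time on azithromycin at follow-up is the same for everyone, and no fixed gap between the two HROMs is promised.
- A reader might infer three mutually exclusive macrolide rules. Section 4.2 is a general exclusion that says nothing about earlier HROMs, and the statements can be read as cumulative. What remains is that the footnote and Section 7.1 differ in both anchor and drug condition, and that Section 4.2 does not close the gap for short courses.
- A reader might infer that HROM completion is inflated. Section 6.1 does not say that pre-trial tests count, and these participants still face the follow-up HROM, which Section 4.4 foresees some declining. Acceptability is a survey judgement, so having had one test does not guarantee a favourable answer. Selection of people who already tolerated HROM is possible, no more.
- A reader might infer that earlier tests used another technique. Recruitment is from one Trust, and nothing shows this. The protocol only fails to tie an accepted earlier test to Section 5.3.

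It can also be said that choosing analysis sets is commonly left to an SAP, which is not shown, and that sparing patients a repeat invasive test is sensible. Both are fair. The point therefore rests on the protocol's differing eligibility statements and on what it allows as a baseline, not on missing analysis detail.

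**Conclusion.** The point holds in a limited form. As written, the protocol pools baseline HROMs of unequal age, up to about 118-120 days before Day 0, and possibly of unequal macrolide exposure. At the extreme, the HROM change spans about 146-162 days against 28-42 days for symptoms. This rests on the screening anchor and on azithromycin starting at Day 0. It applies only to participants with a prior HROM, whose number is not given. The outcomes directly weakened, HROM change and its relation to symptoms, are exploratory.

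The look-back anchor and the macrolide conditions in the schedule footnote, Section 7.1 and Section 4.2 must be reconciled, because they classify some patients differently. For the primary feasibility outcomes the most that can be said is that completion may be inflated, by an amount that depends on counting rules and numbers the protocol does not give, and that acceptability may be affected by selection. The matter should be corrected but does not threaten the study.

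**What to change.** 1. Replace the wording in the schedule footnote, Section 7.1 and Section 4.2 with one consistent statement of the look-back anchor, the macrolide exposure that matters and the period it covers. Which rule to adopt is for the sponsor and investigators.
2. Record on the CRF the date and source of the baseline HROM, whether it met Section 5.3, and any macrolide exposure before or after it.
3. In Section 11, present the paired HROM change and the motility-symptom correlation for participants with a Day 0 HROM beside the analysis of all participants.
4. State in Section 6.1 that only HROMs done within the trial count towards HROM completion, and report completion and acceptability separately for participants with and without a prior HROM. Section 4.4 makes the trial experience survey anonymous, so the acceptability split needs a question on prior HROM on the survey itself.

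The cost is a protocol amendment, a few CRF fields and one survey item. The Day 0-only analysis has fewer pairs: at most 30 - k if k participants enter with a prior HROM. No participant needs an additional HROM.
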